8.8.4 Vital Signs

The following vital signs will be listed and summarized by dose cohort and overall, and by visit for Part 1:

- systolic and diastolic blood pressure (mmHg);
- pulse rate (bpm);
- Pulse Oximetry (%);
- respiration rate (breaths/min);
- body temperature (°C);
- weight (kg);
- BMI (kg/m²).

Temperature will be displayed in degrees Celsius (°C); temperatures recorded in degrees Fahrenheit (°F) will be converted as: [temperature (°C) = (temperature (°F) – 32)×5/9]. Height will be displayed in centimeters (cm); height recorded as inches (in) will be converted as: [height (cm) = height (in)*2.54]. Weight will be displayed in kilograms (kg); weight recorded as pounds (lb) will be converted as: [weight (kg) = weight (lb)*0.45359237]. BMI recorded in pounds and inches will be re-calculated as the following: BMI(kg/m²) = BMI(lb/in²) * 703.

All vital signs data will be listed. For Part 1, vital signs data including blood pressure, pulse rate, pulse oximetry, respiration rate, and temperature and changes from baseline for the following time points will be summarized by dose cohort and visit using standard descriptive statistics:

• Day 1 Pre-Dose;

- Day 1 Post-Dose first measurement;
- First Measurement for Days 2, 3, 4, 8, 15, and 29.

For Part 2, same set of vital sign variables and change from baseline will be summarized by treatment group and the time points below.

- Day 1 Pre-Dose;
- Day 1 Post-Dose first measurement;
- First Measurement for Days 21, 42, 63, 84, 104, 169, and 253.

For both Part 1 and Part 2, the baseline value will be defined as last scheduled or unscheduled value collected prior to the first dose of study treatment. Assessments carried out on day of first study treatment administration are considered to have taken place before the study treatment administration, if the corresponding times have not been recorded. For post-baseline, only data from scheduled visits will be included in the summary tables.

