Vitals will be taken pre-dose, post dose, then every 2 hours until subject leaves the unit. Vital signs (blood pressure, pulse rate, respiratory rate or pulse oximetry, and oral body temperature) will be obtained after the patient has been in a sitting position for 5 minutes. A 12-lead pre-dose ECG will be taken in triplicate, 5 minutes apart, after the patient has been in a supine (resting) position for at least 5 minutes. The ECG will be read locally. An abbreviated physical exam will be performed.

The randomization page in the EDC will be accessed to randomize the subject, visit information will be entered, and the required eCRFs completed. The research pharmacist will be contacted regarding the subject's randomization and for specifics about the timing of the scheduled lumbar puncture and preparation and availability of study drug or placebo necessary for the intrathecal administration of investigational product.

Serum will be collected for PK and ADA analysis as detailed in Section 13.2.

If a lumbar puncture fails to return CSF after two attempts, it is recommended that fluoroscopy be scheduled to assist in achieving successful LP. Likewise, it is recommended that the lumbar puncture procedure be suspended if the CSF sample is bloody or turbid. Decisions regarding the lumbar puncture procedure are at the discretion of the site principal investigator. Additionally, investigators may make an assessment based on a given patient that all LPs will be conducted under fluoroscopy.

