For dosing visits that include neurological exams and questionnaires (e.g. ISNCSCI, GRASSP, SCIM III self-care and mobility), these assessments should be performed prior to dosing. Depending on scheduling considerations, subjects may be asked to return the following day for dose administration. Under this circumstance, nearby overnight accommodations will be arranged for the subject upon request.

Following dosing, patients will remain under the observation of study personnel in the hospital setting (eg, may include infusion center, PACU, recovery suite, observation unit, short stay center) for 4 hours for safety monitoring. Thereafter, if deemed clinically stable by the Investigator, patients may leave the hospital setting. If further safety observation is directed by the investigator, the subject may be directed to remain at a nearby overnight accommodation or home (if within a reasonable distance) and report the next morning for examination or to remain in the hospital stay; if a decision is made to keep the patient overnight for convenience (e.g. travel issues), this hospitalization should not initiate a serious adverse event report (e.g. local alternate accommodations not readily available). Upon completion of the visit, subjects will be given an appointment reminder card that contains the date and time of the follow-up telephone call and for their next visit.

A telephone call to assess status regarding any adverse events will be conducted on Study Day 8.

At Study Visits 3 through 7 (Study Days 21 through 104), subjects will receive either AXER-204 or placebo via slow bolus infusion intrathecal administration.

At Study Visits 3 through 7, (Study Days 21 through 104), 12-Lead ECGs, abbreviated physical examinations vitals will be obtained. Vitals will be taken pre-dose, post dose, then every 2 hours until subject leaves the unit. Serum collection for PK will be obtained pre-dose and 4 hours post-dose, CSF will be collected pre-dose (as part of the dosing procedure), urine pregnancy tests will be administered on all women of childbearing potential. Changes to concomitant medication will be assessed and recorded as well as adverse events and serious adverse events.

At Visit 3 (Study Day 21) the following efficacy assessments will be performed prior to dosing:

• ISNCSCI

At Visits 5 and 7 (Study Days 63 and 104), the following efficacy assessments will be performed prior to dosing in the order listed:

- ISNCSCI

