### 14.2.3. Adverse Events of Special Interest (AESI)

Adverse Events of Special Interest (AESI) for this study include possible allergic/immune reactions to administration of a protein therapeutic, AEs generally associated with lumbar puncture, and theoretical AEs arising from axon growth. No AESI have been identified from non-clinical toxicology studies with AXER-204. The following are considered AEs of Special Interest for this study:

- Immune/Allergic reactions: fever, rash, arthralgia, myalgia, hematuria, proteinuria, serositis, central nervous system complications, and hemolytic anemia. Injection site reactions may occur
- Events relating to the lumbar puncture procedure: infection, postdural puncture headache, bleeding, brainstem herniation, meningitis, back pain, excessive CSF leakage requiring blood patch
- Complicating infections: discitis and vertebral osteomyelitis
- Neurological symptoms or injuries: low back pain, radicular injury, abducens palsy
- Other: late onset of epidermoid tumors of the thecal sac, increased pain, increased spasticity

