2.1.2 Part 2 Placebo-Controlled Repeat Dose

2.1.2.1 Primary Objective

- To evaluate the safety and tolerability of repeat intrathecal lumbar slow bolus infusions of AXER-204 compared to placebo in subjects with CSCI.
- To evaluate the PK of repeat doses of AXER-204 in subjects with CSCI.

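### Post-dose vital signs are tabulated only after the first of six doses, so doses 2 to 6 have no post-dose vital-sign summary in a repeat-dose safety study

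*SAP*

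**What the plan says.** Protocol section 11.2.2 sets the collection rule, once for Visit 2 and again for Visits 3 to 7: "Vitals will be taken pre-dose, post dose, then every 2 hours until subject leaves the unit". Footnote 4 of the Part 2 schedule of events (Table 6) says the same. The later visits are dosing visits: "At Study Visits 3 through 7 (Study Days 21 through 104), subjects will receive either AXER-204 or placebo via slow bolus infusion intrathecal administration". After each dose the subject stays under observation "for 4 hours for safety monitoring".

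For Part 2, SAP 8.8.4 summarises vital signs and change from baseline by treatment group at these time points:

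- Day 1 pre-dose;
- "Day 1 Post-Dose first measurement";
- "First Measurement for Days 21, 42, 63, 84, 104, 169, and 253".

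Everything else goes to listings: "All vital signs data will be listed". Baseline is the last value before the first dose of the study, so it is not reset at later doses.

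**The concern.** The Part 2 primary objective in SAP 2.1.2.1 is "To evaluate the safety and tolerability of repeat intrathecal lumbar slow bolus infusions of AXER-204 compared to placebo in subjects with CSCI". The acute response to doses 2 to 6 is central to that objective, and the vital-sign tables leave it out.

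The protocol itself anticipates reactions on re-exposure. Section 14.2.3 lists among the events of special interest "Immune/Allergic reactions: fever, rash, arthralgia, myalgia", and section 13.2 draws serum for anti-drug antibodies at every dosing visit. Yet post-dose temperature, pulse and blood pressure are compared between arms only after first exposure, before any response to repeat dosing could show.

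The comparison with placebo matters because both arms undergo lumbar puncture with CSF removal at each dose. A table of post-dose values by arm is the direct way to separate an effect of the drug from an effect of the procedure.

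The wording probably came from Part 1. The Part 1 list in the same section has the same form. There it loses no first post-dose reading, because there is only one dose. Applied to six doses, it drops five.

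**Working it through.** The plan states no figure to reproduce. The check sets the collection schedule against the summary time points.

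**Inputs**

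- Dosing days, Protocol 11.2.2 and Table 6: 1, 21, 42, 63, 84 and 104, so 6 doses.
- Order of readings on a dosing day, Protocol 11.2.2: pre-dose, post-dose, then 2-hourly.
- Planned Part 2 enrolment, Protocol 7.2: about 32, so about 16 per arm.
- Part 2 summary time points, SAP 8.8.4: as listed above.

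**Step 1: which reading is tabulated on each dosing day**

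| Day | Dose | Pre-dose tabulated | First post-dose tabulated | 2-hourly tabulated |
|---|---|---|---|---|
| 1 | 1 | yes | yes | no |
| 21 | 2 | yes (first reading) | no | no |
| 42 | 3 | yes (first reading) | no | no |
| 63 | 4 | yes (first reading) | no | no |
| 84 | 5 | yes (first reading) | no | no |
| 104 | 6 | yes (first reading) | no | no |

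The SAP does not itself call the Day 21 to 104 reading pre-dose. That follows from the protocol's order. A post-dose value could take its place only if the pre-dose reading were missing. The SAP does specify post-dose where it means it, on Day 1. It uses the same first-measurement wording for Days 169 and 253, when no dose is given.

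**Step 2: coverage**

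- By dose: 1/6 = 16.7% covered and 5/6 = 83.3% not covered.
- By planned dosing: 32 × 6 = 192 in total; 32 × 1 = 32 covered; 192 − 32 = 160 not covered.
- AXER-204 arm only: 16 × 6 = 96 in total; 16 covered; 80 not covered.
- By reading, assuming a stay of exactly 4 hours with readings post-dose, at +2 h and at +4 h: 6 × 3 = 18 post-dose readings per subject, of which 1 is tabulated.

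**Step 3: does another rule or table fill the gap?**

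- The Part 2 window rule in SAP 7.2 keeps one value per window, chosen by closeness to the scheduled date. It creates no post-dose time point.
- Laboratory data have shift tables and counts of new potentially clinically significant values (SAP 8.8.3). ECGs have a shift to the worst post-baseline interpretation (SAP 8.8.5). Vital signs have neither.
- ECGs are not a dependable substitute. Protocol Table 6 footnote 5 and section 11.2.2 describe Part 2 ECGs as pre-dose, while section 14.1.4 also describes post-dose ECGs at each dosing time point.

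**Step 4: effect of the change on table size**

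SAP 8.8.4 now has 2 + 7 = 9 time points. Adding the first post-dose reading on five more days gives 9 + 5 = 14 and covers 6 of 6 doses. Rows for the largest same-day change come on top of these.

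**The case against.** The best defence is that other outputs already cover the feared event. Fever is an event of special interest, reported to the sponsor within 24 hours. SAP 8.8.2 tabulates treatment-emergent events, events of special interest and lumbar-puncture-related events by treatment group. A febrile reaction after dose 4 that is recorded as an adverse event therefore does reach a between-arm table. All vital signs are listed, and listings for about 32 subjects can be read. The DSMB meets about every three months during dosing and may see more than the SAP provides for. Protocol 15.11 asks only for descriptive safety tabulation where the data warrant, so no protocol requirement is broken and no test or error rate changes.

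Most of this stands, and it limits the seriousness of the point. It does not close the gap. Adverse-event tables show only what an investigator judged to be an adverse event, and listings do not summarise a difference between arms. A modest but consistent post-dose shift in blood pressure, pulse or temperature under AXER-204 would be found by neither. What the DSMB sees is set by a charter outside these documents and does not alter the planned study tables.

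Two further objections are fair in part. The 192 dosings assume full enrolment and no skipped doses, but the 1-in-6 result for the planned schedule does not depend on enrolment. Adding the first post-dose reading alone would close the basic gap, and the largest same-day change goes further. It is still worth having, because the first reading after dosing may precede a reaction that develops during the observation period.

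**Conclusion.** The concern holds. As written, SAP 8.8.4 puts post-dose vital signs in a summary for 1 of 6 doses, which leaves out 160 of 192 planned dosings (83%), or 80 of 96 in the AXER-204 arm. This rests on the protocol's order of readings, with the pre-dose reading taken first. The dosing totals also assume 32 subjects with all six doses given.

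The data are neither lost nor uncollected, and serious or recognised reactions would surface through adverse-event reporting. The defect is confined to the vital-sign tables, where the chosen time points serve the primary objective of repeat-dose safety poorly. It should be corrected, but it does not threaten the validity of any planned test.

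**What to change.** In SAP 8.8.4, replace the Part 2 time points with the following, by treatment group:

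- for each of Days 1, 21, 42, 63, 84 and 104: the pre-dose value, the first post-dose value, and the change between them;
- for the same days: the largest post-dose increase and the largest post-dose decrease from that day's pre-dose value, using all readings until the subject leaves;
- for Days 169 and 253: a single value, as now.

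Keep change from study baseline alongside. The same-day reference is needed because the study baseline is fixed before dose 1 and mixes the acute response with drift over the treatment period.

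The cost is SAP wording, one derived variable and additional table rows. No new data are collected and no alpha is involved, since safety is descriptive. This SAP version is dated 05 August 2022, and its section 10 reports that the Day 169 data had already been unblinded and analysed. The new tables should therefore be labelled as added after that unblinding.

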8.8.5 Electrocardiograms

The following quantitative ECG measurements will be listed and summarized by dose cohort for Part 1 or by treatment group for Part 2 and overall, and by visit:

- heart rate (bpm);
- RR interval (msec), calculated as (60/HR)*1000;
- PR interval (msec);
- QRS interval (msec);
- QT interval (msec);
- Fridericia corrected QT (QTcF) interval (msec), calculated as $QT/\sqrt[3]{RR/1000}$.

Triplicate ECG will be taken in the study. Average values will be computed from available assessments from the triplicate ECGs to be used for data summaries.

The ECG measurements and changes from baseline in ECG will be listed and summarized using standard descriptive statistics.

An overall Investigator assessment of ECG will be listed and summarized as number and percentage of subjects with each assessment category by visit (categories: "normal", "abnormal, not clinically significant" and "abnormal, clinically significant").

Shifts from baseline (normal vs. abnormal, not clinically significant vs. abnormal, clinically significant) to the worst post-baseline interpretation will be presented.

The baseline value will be defined as last scheduled or unscheduled value collected prior to the first dose of study treatment. Assessments carried out on day of first study treatment administration are considered to have taken place before the study treatment administration, if the corresponding times have not been recorded. For post-baseline, only data from scheduled visits will be included in the summary tables.

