#### Safety Endpoints

Changes from pre-treatment will be calculated in a similar fashion as for the efficacy endpoints, but no inferential statistics will be provided for safety endpoints. Shifts from baseline in electrocardiogram (ECG) will be tabulated for heart rate and QTcF. Other endpoints will be assessed according to the scale of the variable.

Pharmacokinetic Endpoints

Concentration data in both blood serum and in CSF will be assessed descriptively over time. Correlation with efficacy and safety outcomes may be performed, as the data warrant.

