## 15.11. Safety Endpoints

The safety analysis will be descriptive in nature. All safety data will be listed, and data will be tabulated by dose (Part 1) and treatment group (Part 2) where the data warrant. Safety data include:

- AEs, including assessment of lumbar infusion site
  - Events occurring prior to the first dose of investigational product or placebo will be defined as pre-treatment events.

- For Part 1, TEAEs will be defined as any AE occurring during or after the injection of study drug. This will therefore include all events occurring through Day 29/ET.
- For Part 2, TEAEs will be limited to those events occurring within 28 days after the last visit.

Incidence of AEs will be summarized for each treatment group/cohort by MedDRA system organ class (SOC) and preferred term, sorted in descending frequency by SOC, and then by preferred term within SOC. These summaries will be given by treatment in separate tables for each of the following TEAE event sets:

- All events
- Treatment related events (defined by a relationship to study drug of possible, probable, or definite).
- Serious adverse events
- Events leading to premature discontinuation from study
- Events by maximum severity
- AEs of Special Interest, ie, events relating to the lumbar puncture procedure (eg, infection, headache, back pain, excessive CSF leakage requiring blood patch).

Other safety outcomes will include:

- Clinical laboratory tests, including hematology, chemistry, metabolic, and urinalysis. Changes over time will be presented. Potentially clinically significant (PCS) ranges will be defined and used to determine the incidence of subjects experiencing newonset PCS laboratory values, where new-onset is defined as a PCS value for a subject following initiation of study treatment for which the subject did NOT have a PCS value for that analyte PRIOR to initiation of study treatment.
- Vital signs including: respiratory rate or pulse oximetry, heart rate, temperature, and blood pressure, as per the schedule of events. BMI will be assessed, with height collected only at screening.
- Physical examination
- 12-lead ECG. ECG parameters will be analyzed in a fashion similar to that of clinical laboratory parameters.

Condition-specific safety outcomes will include:

- ISNCSCI, GRASSP and all of the neurological measures evaluated for efficacy

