- Spasticity (Modified Ashworth Scale). A clinician administered examination for spasticity which measures muscle tone. A score of 0-4 is assigned to each muscle group evaluated. Note: Testing will exclude fingers and thumb.
- Pain (BPI). A self-administered questionnaire used to assess the severity of a subject's pain and the impact of this pain on the subject's daily functioning.

Concomitant treatments will be assessed according to the timing of their start/stop dates as they relate to the study drug treatment, as follows:

- Prior. Medications with start AND stop date before date of first dose of study drug or placebo.
- Concomitant. Medications with subject exposure that includes at least one dose of study drug or placebo.
- New-onset medications. Concomitant medications with a start date AFTER the first dose of study drug or placebo. New-onset medications are a subset of the full set of concomitant medications.
- Post-treatment medications. Medications with a start date at least 28 days AFTER the last dose of study drug or placebo.

Changes from pre-treatment will be calculated in a similar fashion as for the efficacy endpoints, but no inferential statistics will be provided for safety endpoints. Shifts from baseline in ECG will be tabulated for heart rate and QTcF. Other endpoints will be assessed according to the scale of the variable.

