8.1 General Principles

- All data processing, summarization and analyses will be performed using SAS Environment / Version 9.4 (or later) of the SAS[®] statistical software package.
- The following principles will be applied to all TFLs unless otherwise stated:

Table 6 Statistical Analysis General Principles

Principle	Value
Significant tests	Two sided and use a 5% significance level
Treatment group labels and order	Part 1: AXER-204 xx mg
presented	Part 2: AXER-204 200 mg; Placebo
Tables	Data in summary tables presented by dose
	cohort/treatment group, assessment (where
	applicable), and visit (where applicable).

Principle	Value
Listings	All data collected presented by dose
	conort/treatment group, subject, and visit (where applicable) unless otherwise specified
Descriptive summary statistics for	Number of subjects (N), mean, standard deviation
continuous variables	(SD), median, minimum, maximum.
Descriptive summary statistics for categorical variables	Frequency counts and percentages [n (%)]
Denominator for percentages	Number of subjects in the analysis population, unless otherwise specified.
Include "Missing" as category	Yes, when the number missing is greater than zero for at least one dose cohort/treatment group.
Display for percentage	One decimal place, except for 100%
Display for 0 percentages	0
Display to one more decimal place than collected value	Mean, Median, Mean Difference
Display to two more decimal places than collected value	Standard Deviation
Limit of precision for displays	3 decimal places
Date Format	DDMMMYYYY
TFL orientation	Landscape
TFL output	For all tables and listings, 2.54 cm for the
	top/bottom/left/right margins and 8-point Courier New font

• For both safety and efficacy analysis, the baseline value will be defined as the last non-missing value before the first dose of study treatment.

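### The SAP omits, without declaring it, the protocol's heart rate and QTcF shift tables, so subjects moving from normal to abnormal are not counted by arm or cohort

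*SAP*

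**What the plan says.** **Protocol.** The safety paragraph of the synopsis says: "Shifts from baseline in electrocardiogram (ECG) will be tabulated for heart rate and QTcF". Section 15.11 repeats it: "Shifts from baseline in ECG will be tabulated for heart rate and QTcF". Neither statement carries a condition. Section 15.11 also says "ECG parameters will be analyzed in a fashion similar to that of clinical laboratory parameters", and the laboratory approach it describes includes counting subjects with new-onset potentially clinically significant values.

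**SAP 8.8.5.** Six numeric measurements (heart rate, RR, PR, QRS, QT and QTcF) are listed and summarized by cohort or treatment group and by visit, using the average of the triplicate readings. For changes, the text is: "The ECG measurements and changes from baseline in ECG will be listed and summarized using standard descriptive statistics". SAP 8.1 defines those statistics as N, mean, SD, median, minimum and maximum. The investigator's overall assessment is tabulated by visit, and the only shift table is built on it: "Shifts from baseline (normal vs. abnormal, not clinically significant vs. abnormal, clinically significant) to the worst post-baseline interpretation will be presented". After baseline, only scheduled visits enter the summary tables.

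**SAP section 9.** The declared changes from the protocol concern a secondary endpoint, exploratory endpoints and analysis populations. ECG is not among them.

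**The concern.** Safety and tolerability of repeat dosing against placebo is a primary objective of Part 2. Under the protocol, safety is described and not tested, so counts by arm are the main between-arm evidence. A shift table for a named parameter is such a count: it shows how many subjects began in one category and reached a worse one. The protocol names the two parameters, and the SAP does not produce the tables.

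The investigator's reading does not stand in for them. It grades the whole ECG, is made locally at about five centers, and is not tied in either document to any QTcF or heart rate value. A subject already graded abnormal at baseline for another reason could develop a longer QTcF without changing grade.

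Because section 9 is silent, a reader of the study report could not tell whether the tables were dropped on purpose or overlooked. The laboratory section of the SAP does carry out its half of the commitment (reference-range shifts and new-onset counts in 8.8.3), which makes an oversight plausible.

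**Working it through.** The plan gives no figure to reproduce. The check sets the two documents side by side and then asks what the retained tables can show.

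**1. Commitment against delivery**

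| Item | Protocol synopsis and 15.11 | SAP 8.8.5 |
|---|---|---|
| Shift from baseline, heart rate | Yes | No |
| Shift from baseline, QTcF | Yes | No |
| Shift of investigator's overall reading | Not named | Yes, to worst post-baseline |
| Numeric values and changes by visit | Changes from pre-treatment | Yes, including maximum |
| Subject listings | Yes | Yes |
| Omission declared in SAP section 9 | n/a | No |

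**2. What the by-visit table shows for one subject**

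Inputs: about 16 subjects per arm in Part 2 (Protocol 7.2) and 6 per cohort in Part 1. I assume a rise of 30 or 60 ms in one subject and no change in the others. These sizes are illustrative and come from neither document.

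- Effect on the arm mean, Part 2: 30/16 = 1.9 ms; 60/16 = 3.75 ms.
- Effect on the cohort mean, Part 1: 60/6 = 10 ms.
- Maximum of the change row at that visit: 30 or 60 ms.

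The mean dilutes the case, but the maximum shows it in full. A single prolongation at a scheduled visit is visible.

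**3. What the by-visit table cannot show**

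Part 2 schedules ECGs at seven post-baseline visits: Days 21, 42, 63, 84, 104, 169 and 253 (Protocol Table 6). Suppose that at each visit exactly one of the 16 subjects in an arm has a 60 ms rise and the other 15 have none. Every visit's change row then has N = 16, mean 3.75, median 0, minimum 0, maximum 60 and the same SD. Two quite different situations give this same table:

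- the same subject at all seven visits: 1/16 = 6.25% of the arm ever affected;
- a different subject at each visit: 7/16 = 43.75% ever affected.

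A baseline-to-worst shift table would separate them, provided the rise crosses a category boundary. The by-visit statistics cannot, because SAP 8.8.5 takes a worst post-baseline view only of the investigator's reading.

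The row of QTcF values and the row of changes can also reach their maxima in different subjects. Movement from normal to prolonged therefore cannot be read from the two rows together.

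**The case against.** A reader might infer that, with the shift tables gone, an individual QTcF prolongation appears in no ECG summary, or that only the investigator's normal or abnormal grade survives. The documents do not support either inference. SAP 8.8.5 keeps six numeric parameters and their changes by visit, SAP 8.1 includes the maximum, and every value is listed in a study of about 32 subjects in Part 2 and up to 24 in Part 1. The dilution of the mean in the working is no evidence of a hidden case, because the same row reports the maximum.

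Other safeguards also stand. Protocol 14.1.4 requires clinically significant ECG abnormalities after dosing to be recorded as adverse events, which then enter the tables of SAP 8.8.2. That route is narrower for findings first seen at Day 169 or later. SAP 8.8.2 closes the treatment-emergent window 28 days after the last injection, and Day 169 is 169 − 104 = 65 days after the last planned dose.

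The commitment should not be stretched. Only the heart rate and QTcF shifts are explicit. That ECG analysis should also count new-onset potentially clinically significant values is a fair reading of the comparison with laboratory parameters, but the protocol gives no ECG range, QTcF category or change threshold. Any particular cut-off comes from outside the documents.

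On materiality, the protocol's list of adverse events of special interest has no cardiac item, off-target systemic toxicity is not anticipated, and no decision rule depends on the missing tables. This limits the weight of the point. It does not explain why a promised analysis is absent and undeclared.

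**Conclusion.** The point holds as an undeclared mismatch between protocol and SAP on a safety analysis. Two promised shift tables are missing. The consequence is limited: the extreme value per arm and scheduled visit can be seen and listings exist, but the number of subjects whose heart rate or QTcF moved from normal at baseline to abnormal at any later visit is not tabulated by arm or cohort. In the illustration, by-visit change statistics fit anything from 1 of 16 to 7 of 16 subjects ever affected; resolving that would need a hand count from the listings. The illustration assumes 16 evaluable subjects per arm at every visit, one affected subject per visit and a 60 ms rise.

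The tables should be restored, because the commitment was stated twice, serves a primary objective and is cheap to honor. Nothing here suggests that a cardiac signal exists or that one would be concealed.

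**What to change.** In SAP 8.8.5, add shift tables from baseline category to worst post-baseline category for QTcF and for heart rate. Use the triplicate mean and present them by cohort in Part 1 and by arm in Part 2. The sponsor chooses the categories and writes them down before the final Day 253 lock.

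The SAP should state that the categories were set after the Part 1 and Day 169 outputs. SAP 2.2 places the Part 1 outputs at the Part 1 lock and all Part 2 safety summaries at the Day 169 unblinding, and SAP section 10 already reports Day 169 efficacy results. The categories cannot be presented as prespecified for those stages.

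Counts of subjects with a QTcF change above stated thresholds are an optional addition. If the sponsor prefers not to produce the shift tables, section 9 should list the omission with a reason.

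Cost: about two tables, from data already collected, with no change to procedures or visits.
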